- The proportion of subjects who received at least one dose of the intervention and who exhibit an increase in liver function tests from baseline (pre-treatment Day 1) as defined as: confirmed AST elevation of >5X ULN or greater than or equal to 225 IU/L or ALT elevation of >5X ULN or greater than or equal to 250 IU/L or total bilirubin elevation >1.5X ULN or aminotransferase elevation of >3X ULN accompanied by total bilirubin elevation >1.5X ULN.

Exploratory Outcome 8:

- The adherence to long term self-administration of daily medications will be assessed in this order of precedence:
 - First: The mean number of pills taken as assessed by pill-count on Days 22, 29 and 43.
 - Second: Subject self-reported adherence as reported on Days 22, 29 and 43.

Exploratory Outcome 9:

- The proportion of subjects with a detectable fluconazole level as assessed by blood test on Days 22 and 43 in fluconazole recipients.
 - Plasma fluconazole concentration will be determined by high-performance liquid chromatography (HPLC)

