11. Current diagnosis and/or treatment of active liver disease including abnormal baseline liver function tests as defined as: total bilirubin greater than or equal to 3.0mg/dL AND either AST greater than or equal to 135 IU/L OR ALT greater than or equal to 150 IU/L.
 12. On hemo or peritoneal dialysis or have a creatinine of ≥ 2.0 mg/dL or estimated CrCl ≤ 50 mL/min.
 13. History of hypokalemia defined as less than 3.5 mEq/L on more than one occasion during the 4 weeks prior to enrollment.
 14. History of cardiovascular disease with increased risk for torsades de pointes as defined as:
 - a. NYHA Heart Failure Criteria III or greater; OR
 - b. History of atrial or ventricular dysrhythmias; OR
 - c. History of structural heart disease (including previously repaired); OR
 - d. Personal or family history of congenital long QT syndrome.
 15. A marked baseline prolongation of the QT/QTc interval as defined as a QTc interval > 450 milliseconds (ms) for male subjects or > 470ms for female subjects with repeated demonstration*.

* Subjects without a history of prolonged QTc and an abnormal baseline QTc interval should undergo repeat ECG assessment within screening period prior to randomization (72 hours) to confirm prolongation. If the repeat ECG QTc is within normal limits and less than the parameters above, the subject may be considered for enrollment.
 16. Pregnant or lactating females.
 17. History of azole intolerance or allergy.
 18. Individuals for whom study participation would not be in their best interest, as determined by the clinical investigator.
 19. Are taking medications that are contraindicated with concurrent use of fluconazole (See Section 6.6.1: Contraindicated Medications).
 20. Positive point of care HIV test at Day 1 visit consistent with new HIV diagnosis.

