11.4.3. Safety Analysis Plan

Safety evaluations will be based on the incidence, severity, and type of clinically significant physical examination findings, clinically significant vital signs, and SAEs as defined in Section 9.2.2. Safety variables will be tabulated and presented for all subjects in the safety population, grouped by treatment group.

SAEs will be coded by the Medical Dictionary for Regulatory Activities (MedDRA) for preferred term and system organ class. The rate and exact 95% confidence intervals of related SAEs in aggregate, and by MedDRA categories, will be computed. The number of SAEs will be reported by a detailed listing showing the type, MedDRA coding, relevant dates (administration and adverse event), severity, relatedness, and outcome for each event.

Laboratory toxicities will be analyzed by taking the most severe response over the follow-up period, dichotomizing into a binary variable (none or mild versus moderate or severe) and using exact confidence intervals to summarize the event and toxicity rates. Tabular and graphical summaries of events will be presented for each solicited symptom, by type, severity (none, mild, moderate, severe), and time point post-administration.

Laboratory and vital sign data will also be presented as change from baseline. Variable transformations will be applied as appropriate. Shift tables may be produced for select laboratory parameters.

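### Exploratory Outcome 7 is labelled a rise in liver tests from Day 1, but its limits contain no Day 1 comparison, so a stable abnormal value can count as an event (minor)

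*Combined protocol and SAP*

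**What the plan says.** Section 3.2.3 gives the numerator of Exploratory Outcome 7 as subjects who "exhibit an increase in liver function tests from baseline". It takes baseline as Day 1 before treatment, and defines such an increase as any of the following:

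- "confirmed AST elevation of >5X ULN or greater than or equal to 225 IU/L"
- "ALT elevation of >5X ULN or greater than or equal to 250 IU/L"
- "total bilirubin elevation >1.5X ULN or aminotransferase elevation of >3X ULN accompanied by total bilirubin elevation >1.5X ULN"

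The last line holds two limits: bilirubin alone, and bilirubin with an aminotransferase. The denominator is everyone dosed: "The proportion of subjects who received at least one dose of the intervention". Nothing removes subjects who were over a limit before dosing.

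The laboratory part of exclusion criterion 11 (Section 5.2) is a joint rule: "total bilirubin greater than or equal to 3.0mg/dL AND either AST greater than or equal to 135 IU/L", or the same bilirubin with ALT at or above 150 IU/L. The criterion also excludes diagnosed or treated active liver disease.

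Section 11.4.3 requires laboratory data to be shown as change from baseline, and laboratory toxicities to be summarised by worst severity with exact confidence intervals. It then adds: "Shift tables may be produced for select laboratory parameters".

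**The concern.** The label and the definition of the outcome do not match. The label describes a change since Day 1. The definition describes a state at follow-up. A subject who enters with a stable raised bilirubin, or a stable raised AST or ALT, is in that state at the first confirmed follow-up test without any change.

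Outcome 7 is the measure attached to the exploratory objective on liver safety (Section 3.1.3). Non-serious adverse events are not collected (Section 9.2.1), and Section 9.2.2 narrows serious events to birth defects and unexpected events attributed to the drug. An expected liver effect of fluconazole will therefore be seen mainly in laboratory data. If the headline proportion mixes existing abnormalities with new ones, its level is too high in both arms and the ratio between arms is pulled towards 1. Two analysts could also count different events from the same data, depending on whether they treat the label as a condition.

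**Working it through.** The plan gives no expected rate, power or significance level for Outcome 7, so there is no figure to reproduce. The check has three steps.

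**1. Does the definition use Day 1 at all?** Each of the four limits depends only on the current value and the ULN, or on a fixed number. The fourth (aminotransferase above 3 x ULN with bilirubin above 1.5 x ULN) lies wholly inside the third (bilirubin above 1.5 x ULN alone), so an unchanged bilirubin is enough. Confirmation does not help, because a stable value confirms on repeat. Elsewhere the protocol writes a baseline term when it wants one: response is a percentage reduction from baseline (Section 3.2.1), the QTc rule includes a rise above the baseline measurement (Sections 5.3.3.1, 9.2.3 and 9.5), and Table 4 requires a negative Day 1 test before a later positive one counts.

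**2. Can a subject over a limit enter?** If 225 and 250 IU/L represent 5 x ULN, the implied ULN is 225/5 = 45 for AST and 250/5 = 50 for ALT. The exclusion values are then 135/45 = 3 and 150/50 = 3 times ULN. The bilirubin ULN is not given, so 1.0 to 2.0 mg/dL is assumed. Each profile below is held unchanged from Day 1 to follow-up.

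| AST / ALT (IU/L) / bilirubin (mg/dL) | Excluded by laboratory rule? | Outcome 7 event if unchanged? |
|---|---|---|
| 230 / 40 / 0.8 | No | Yes, at every bilirubin ULN tried |
| 40 / 260 / 0.8 | No | Yes, at every bilirubin ULN tried |
| 40 / 40 / 3.5 | No | Yes, at every bilirubin ULN tried |
| 40 / 40 / 2.5 | No | Yes at ULN 1.0 to 1.5; no at 2.0 |
| 140 / 40 / 2.5 | No | Yes at ULN 1.0 to 1.5; no at 2.0 |
| 140 / 40 / 3.2 | Yes | Not enrolled |
| 30 / 30 / 0.8 | No | No |

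So the route in exists for a single abnormal test.

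**3. How large could the effect be?** Let b be the share of subjects over a limit on Day 1 who stay there, and i the rate of new events in the rest. The counted rate is b + (1 - b) x i, and the difference between arms is (1 - b) x (i1 - i0). The illustration uses 500 per arm (Table 1) and assumed new-event rates of 1% on placebo and 3% on fluconazole. The standard error of the difference is the square root of [p0(1 - p0) + p1(1 - p1)]/500.

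| b | Counted without change, per arm | Placebo | Fluconazole | Ratio | Difference (points) | SE (points) |
|---|---|---|---|---|---|---|
| 0% | 0 | 1.00% | 3.00% | 3.0 | 2.00 | 0.88 |
| 1% | 5 | 1.99% | 3.97% | 2.0 | 1.98 | 1.07 |
| 2% | 10 | 2.98% | 4.94% | 1.7 | 1.96 | 1.23 |
| 3% | 15 | 3.97% | 5.91% | 1.5 | 1.94 | 1.37 |
| 5% | 25 | 5.95% | 7.85% | 1.3 | 1.90 | 1.60 |

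For example, at b = 5% the placebo rate is 0.05 + 0.95 x 0.01 = 0.0595.

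With assumed new-event rates of 2% and 5% instead, the ratio falls from 2.50 to 2.00, 1.74 and 1.41 at b = 1%, 2% and 5%, and the difference from 3.00 to 2.97, 2.94 and 2.85 points.

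**The case against.** **The label may be a condition.** The phrase about an increase from Day 1 can be read as an extra requirement on top of the limits, and that reading gives the words a purpose. It is possible, but the text joins label and limits as a definition and states no size of rise. What remains is at least an ambiguity that changes the count.

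**Baseline comparisons are already planned.** A reader might infer that liver tests will not be compared with Day 1 at all, or that Outcome 7 is the only look at liver safety. Neither is so. Section 11.4.3 requires change from baseline and a worst-severity summary. Section 9.2.3 sends aggregate hepatic abnormalities to the DSMB, Section 9.6.2 allows it unblinded rates, and Section 9.5 has a halting rule. None of this is tied to Outcome 7, though, and the shift tables are optional.

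**Power.** With 1% and 3% assumed, a two-sided 5% Z test has 62% power at b = 0 and 22% at b = 5%. It is tempting to call this a loss of power, but no test is planned for Outcome 7. It asks for a proportion, so those figures bear on no stated analysis.

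**Few may be affected.** The clinical part of exclusion 11, investigator discretion (exclusion 18) and the review of screening results before randomization (Section 7.2) will remove some of these subjects. This stands: the number could be close to zero.

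**A new-onset definition can lose signal.** A subject over a limit on Day 1 whose value then climbs would never be an event on that test, and Section 9.1 singles out previous liver injury as a setting for toxicity. This also stands, and it shapes the fix.

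**A separate analysis plan may settle it.** Sections 11.4.4 and 11.4.4.3 defer exploratory efficacy analyses to a document not supplied here. Whether it covers this safety outcome is unclear.

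**Conclusion.** The mismatch is real and minor. As written, Outcome 7 can count a stable Day 1 abnormality as an event, and the laboratory part of exclusion 11 lets such subjects in when only one test is abnormal. The consequence is an inflated proportion in both arms, a diluted ratio and a wider interval. In the 1% and 3% illustration, the ratio falls from 3.0 to between 2.0 and 1.3 as the Day 1 prevalence goes from 1% to 5%, while the difference falls by at most 0.10 points.

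A reader might infer that the comparison between arms is biased in one direction. It is not: Day 1 status precedes randomized treatment, so these subjects should fall about equally in both arms.

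The size rests on assumed event rates, an assumed prevalence and the assumption that Day 1 abnormalities persist. The documents give none of these, and at zero prevalence there is no effect. The eligibility finding depends on an assumed bilirubin ULN for some profiles, but not for the isolated AST, ALT and 3.5 mg/dL bilirubin profiles.

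**What to change.** Three changes to the analysis definition:

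1. In Section 3.2.3, count an Outcome 7 event, test by test, when a confirmed post-dose value meets a listed limit that the same subject's Day 1 value did not meet. A subject with raised Day 1 bilirubin can then still have a new AST or ALT event. Treat the qualifying pre-dose panel as Day 1 where Sections 7.1 and 7.2 allow one from the preceding 72 hours.
2. Tabulate by arm, not only list, subjects already over a limit on Day 1, with the number who rose further above their Day 1 value.
3. In Section 11.4.3, make the shift table from Day 1 to worst post-dose value, by arm, mandatory for AST, ALT and total bilirubin.

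In the illustration, stable abnormal subjects become non-events. At b = 5% the rates are 0.95 x 1% = 0.95% and 0.95 x 3% = 2.85%, and the ratio returns to 3.0.

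The alternative of counting any value that meets a limit and exceeds Day 1 would keep worsening subjects in the headline figure. With no size of rise stated, however, it would also count trivial upward fluctuation.

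The cost is small: one line of definition and two tables, from a panel already collected at screening and on Days 22, 29 and 43. The downside is that worsening in subjects already over a limit appears in a separate table and not in the headline proportion. The same four limits also govern stopping of drug and halting (Sections 5.3.3.1, 9.2.3 and 9.5). The sponsor should reconcile those passages and exclusion 11 with the outcome. No clinical threshold is proposed or altered here.

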3.1.3. Exploratory

- To assess the effect of early empiric fluconazole therapy on the immune response to coccidioidomycosis in subjects with suspected coccidioidomycosis pneumonia.
- To assess the effect of early empiric fluconazole therapy on the development of extrapulmonary symptoms associated with coccidioidomycosis pneumonia.

-
- To assess the effects of early empiric fluconazole therapy on the occurrence of disseminated coccidioidomycosis in subjects with pneumonia in coccidioidomycosis-endemic areas.
 - To characterize the natural history of coccidioidomycosis disease by examining the clinical response and its individual components over time, in placebo recipients with coccidioidomycosis pneumonia.
 - To assess the clinical response of early empiric antifungal therapy with fluconazole at Day 22 in subjects with coccidioidomycosis pneumonia based on an alternative serologic case definition for coccidioidomycosis pneumonia.
 - To compare the clinical signs and symptoms of community-acquired pneumonia caused by coccidioidomycosis pneumonia with the clinical signs and symptoms caused by non-coccidioidomycosis pneumonia in coccidioidomycosis-endemic areas.
 - To characterize the safety of early empiric antifungal therapy with fluconazole with respect to liver function in subjects with pneumonia in coccidioidomycosis-endemic areas.
 - To assess the adherence to long term self-administration of daily fluconazole or placebo in a clinical trial setting using self-reported adherence and pill count.
 - To assess medication adherence in the active fluconazole arm by measuring fluconazole levels.

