This primary analysis will be performed in the cocci-positive per-protocol population of subjects who meet the case definition of coccidioidomycosis pneumonia and who were adherent to the intervention administration (See Section 11.4.1). As defined below, adherence will be defined as taking at least 80% of the study medication (fluconazole or placebo) as determined at the day 22 visit. Pill count, if available, will take precedence over patient report of adherence.

Case Definition

The case definition of coccidioidomycosis pneumonia is met if the is subject diagnosed with CAP at the time of enrollment as determined by the referring health care provider, and meets one of the following serologic criteria:

1. The patient is positive for any two serologic tests at any time point from Day 1 through Day 29. The two positive results can but do not necessarily have to be from the same assay or the same time point. The assays considered for this criteria are: Immunodiffusion testing [IDTP (IgM) and IDCF (IgG)]; Enzyme linked immunoassay testing (EIA-IgM and EIA-IgG); OR
2. The patient is negative for anti-*Coccidioides* antibody by immunodiffusion assay (or EIA-IgG) at Day 1 and sero convert to positive for anti-*Coccidioides* antibody by immunodiffusion assay (or EIA-IgG) at any time point after Day 1 through Day 29; OR
3. The patient is negative or indeterminate for anti-*Coccidioides* antibody by CF assay on Day 1 and demonstrates a titer of greater than or equal to 2 by CF assay at any point after Day 1 through Day 29; OR
4. The patient is positive for anti-*Coccidioides* antibody by CF assay on Day 1 and demonstrates a rise of greater than or equal to 2-fold dilution in Complement Fixation (CF) titer compared to baseline at any time point after Day 1 through Day 29.

All serologic testing for a single participant from Day 1 through Day 29 will be batched and run concurrently to eliminate confounding due to test run variability.

Adherence

Adherence in all subjects will be assessed by patient self-report and pill count according to standard procedures, on Days 22, 29 and 43. Pill count, if available, will take precedence over patient report. If pill count is not available, patient report will be used.

To be considered adherent at a visit when the clinical response is measured, the subjects will need to have taken at least 80% of their expected pills.

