6.2. Dosage, Preparation and Administration of Study Intervention/Investigational Product

Fluconazole

Fluconazole 400 mg (administered orally as two 200mg capsules) once daily for a minimum of 42 days.

Pills should be maintained as dispensed and not scored, cut, crushed, or otherwise divided for ease of swallowing. The capsules will be administered with water sufficient for the subject to swallow the required number of capsules.

Placebo

Placebo (administered orally as two matching placebo capsules) once daily for a minimum of 42 days.

Pills should be maintained as dispensed and not scored, cut, crushed, or otherwise divided for ease of swallowing. The capsules will be administered with water sufficient for the subject to swallow the required number of capsules.

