7.3. Follow-up (Days 22-180, Visits 02-07)

7.3.1. Follow-up Visit Visit 02 (Day 22):

(Window: Day 20 to Day 23):

- Interview subjects and review the medical record for interim medical history, including an assessment for new medical conditions and symptoms, hospitalizations, diagnosis of disseminated coccidioidomycosis. Note any changes since the previous clinic visit.
- Perform a urine or serum pregnancy test on all women of childbearing potential. The test must be negative to ensure continued eligibility.
- Review any concomitant medications since previous study visit. Record all concomitant medications on the appropriate data collection form.
- Review of inclusion/exclusion criteria by clinician licensed to make medical diagnoses to determine continued eligibility.

-
- Perform a targeted physical examination if indicated based on review of complete medical history and any updates obtained by interview of subjects since the Day 1 visit by a clinician licensed to make medical diagnoses.
 - Record vital sign measurements (sitting blood pressure, sitting heart rate, respiratory rate, oral temperature, oxygen saturation and weight).
 - Query subject regarding whether the subject has taken their dose for today. If the subject has not yet taken their dose for today, subject should be instructed to take the day's dose in the clinic, prior to the pill count.
 - Perform a pill count of study product (fluconazole or placebo) and interview to determine adherence. Review need to bring pill bottles for count to each visit, study product dosing and storage requirements and ability to meet requirements with subject.
 - Following pill count, collect the pill bottle A and retain until study product accountability has been completed by the study monitor.
 - Note any discrepancies between expected and actual pill count remaining in pill bottle B.
 - Review randomization number assigned at Visit 01 and dispense final bottle (bottle C) of study product. Instruct the subject to continue to take daily doses from pill bottle B and to begin taking their daily doses from the newly dispensed bottle (bottle C) once bottle B is empty.
 - If subject did not return the pill bottle A dispensed at Visit 01, instruct them to return this bottle at their next visit.
 - Complete FLEET CAP Score
 - Collect the number of days missed from school and/or work due to illness for subjects who were either enrolled in school or employed at baseline

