11.4. Final Analysis Plan

11.4.1. Analysis Populations

Safety Analyses:

- Safety population – This safety analysis population includes all subjects who took at least one dose of study medication.

Efficacy Analyses:

- Intent-to-Treat (ITT) population – This efficacy analysis population includes all randomized subjects.
- Cocci Positive Modified Intent-to-Treat (mITT) population – This efficacy analysis population includes all randomized subjects who meet the case definition of coccidioidomycosis pneumonia and took at least one dose of study medication. Note that it is not necessary for a subject to be adherent to study drug to be eligible for inclusion in the mITT population.
- All Randomized Modified Intent-to-Treat (mITT) population – This efficacy analysis population includes all randomized subjects who took at least one dose of study medication regardless of cocci-status. Note that it is not necessary for a subject to be adherent to study drug to be eligible for inclusion in the mITT population.

- Cocci Positive Per-Protocol (PP) population – This efficacy analysis population includes randomized subjects who meet the case definition of coccidioidomycosis pneumonia who were compliant with the intervention administration and have coccidioidal serology data available at the Day 1 and 22 visits.
- All Randomized Per-Protocol (PP) population – This efficacy analysis population includes randomized subjects who were compliant with the intervention administration regardless of cocci-status and have coccidioidal serology data available at the Day 1 and 22 visits.

Adherence is assessed at each study visit depending on the fraction of expected pills taken on or before that time point. If at any visit the subject's cumulative fraction of pills taken drops below 80%, they are deemed non-adherent. This decision is not reversible, even if the subject's cumulative fraction of pills taken rises above 80% at a future visit.

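### Exploratory Outcome 8 reports adherence as a mean pill count with no denominator, so visit timing and protocol-required stops shift it without any missed dose

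*Combined protocol and SAP*

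**What the plan says.** The objective in Section 3.1.3 is "To assess the adherence to long term self-administration of daily fluconazole or placebo in a clinical trial setting using self-reported adherence and pill count". Section 3.2.3 turns it into Exploratory Outcome 8, with two measures in order of precedence: "First: The mean number of pills taken as assessed by pill-count on Days 22, 29 and 43", then "Second: Subject self-reported adherence as reported on Days 22, 29 and 43". The first is a count. The outcome gives it no denominator, no adjustment for the actual visit date and no rule for subjects taken off drug. The second has no stated scale.

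Elsewhere adherence is relative. Section 3.2.1 assesses it in all subjects at the same three visits and requires that "the subjects will need to have taken at least 80% of their expected pills". Section 11.4.1 uses the same idea for the per-protocol populations: "Adherence is assessed at each study visit depending on the fraction of expected pills taken on or before that time point".

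Three other parts of the plan decide how many capsules a subject can have taken:
- **Dose and duration.** Section 6.2 has "Fluconazole 400 mg (administered orally as two 200mg capsules) once daily for a minimum of 42 days", while Section 4 gives the treatment period simply as 42 days.
- **Visit windows.** These are Day 20 to 23 (Section 7.3.1), Day 27 to 30 (Section 7.3.2) and Day 42 to 46 (Section 7.3.3).
- **Stopping.** Section 5.3.3.1 lists reasons for taking a subject off treatment while follow-up continues, among them liver, QTc, pregnancy, SAE and hospitalization criteria.

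**The concern.** A mean count measures adherence only if every subject could have taken the same number of capsules by the visit. Here that number varies in two ways.

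First, it depends on the day within the window on which the subject is seen. Second, it depends on whether study drug was stopped under the protocol. A subject who took every dose until a required stop, and who still attends Day 43, enters the mean with a low count and looks like someone who skipped doses.

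The summary would then mix pill-taking behaviour with scheduling and with discontinuation. It also cannot show what share of subjects met the protocol's own 80% criterion. What is at stake is how one exploratory adherence result is read.

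**Working it through.** The plan states no expected value for Exploratory Outcome 8, so there is no figure to reproduce. I read the count as cumulative from Day 1.

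**Inputs.** Two capsules daily (Section 6.2). First dose observed on Day 1 (Section 7.2). The visit-day dose is taken before the Day 22 and Day 29 counts (Sections 7.3.1 and 7.3.2). Windows as above. Three bottles of 34 capsules (Sections 6.1.2, 7.2 and 7.3.1), a supply of 102.

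**Visit timing.** Capsules taken with perfect intake = 2 × days of dosing up to and including the visit.

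| Visit | Earliest day | Nominal day | Latest day | Spread |
|---|---|---|---|---|
| Day 22 | 2 × 20 = 40 | 2 × 22 = 44 | 2 × 23 = 46 | 6 (6/44 = 13.6%) |
| Day 29 | 2 × 27 = 54 | 2 × 29 = 58 | 2 × 30 = 60 | 6 (6/58 = 10.3%) |
| Day 43, dosing ends at 42 days | 84 | 84 | 84 | 0 |
| Day 43, dosing continues to the visit | 84 | 86 | 92 | 8 (8/86 = 9.3%) |

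Forty capsules is therefore 40/40 = 100% of expected on Day 20 but 40/46 = 87% on Day 23. The two Day 43 rows correspond to the two statements of duration, and the supply of 102 would cover either. Section 7.3.3 does not repeat the instruction to take the day's dose before the count, so a visit on Day 42 could also show 82.

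**Protocol-required stops.** Assume perfect intake until the stop and 84 capsules in everyone else. With a fraction f stopped after Day s, the Day 43 mean is (1 − f) × 84 + f × 2s. The documents give neither f nor s, so both are assumptions.

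| Stop | f = 2% | f = 5% | f = 10% |
|---|---|---|---|
| After Day 22 (44 capsules) | 83.2 | 82.0 | 80.0 |
| After Day 8 (16 capsules) | 82.6 | 80.6 | 77.2 |

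For example, 0.90 × 84 + 0.10 × 44 = 80.0, which is 95% of 84, and 0.90 × 84 + 0.10 × 16 = 77.2, which is 92%. The Day 22 row fits stops prompted by scheduled liver tests, because the first on-treatment safety labs are at that visit (Section 8.2.1). Other stopping reasons can arise earlier.

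**Does a percentage cure both problems?** Dividing by capsules expected to the visit removes the timing effect at Days 22 and 29. It does not by itself deal with stops: a subject stopped after Day 22 scores 44/84 = 52% at Day 43 if expected pills run to the end of dosing, and 44/44 = 100% if they end at the stop. Nor may the denominator run past the end of dosing: if dosing ends at 42 days, a perfect taker seen on Day 46 would score 84/92 = 91%.

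**The case against.** The strongest reply is that adherence against expected pills is already recorded. Section 3.2.1 assesses the 80% criterion in all subjects at Days 22, 29 and 43, and Exploratory Outcome 9 adds drug levels in fluconazole recipients. This stands. A reader might infer that the trial cannot describe adherence at all, or that its two adherence measures contradict each other. The documents support neither: a count and a fraction are two summaries of the same pill count, and the needed information exists for every subject.

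Visit timing should balance between randomised arms that stay blinded through the Day 43 assessments, and it vanishes at Day 43 if dosing ends at 42 days. This also stands. The 40-to-46 range describes individuals at opposite ends of a window and is not a difference between arm means.

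A reader might further infer a biased comparison between arms. Stops could differ by arm, since randomisation does not balance events after baseline, but the documents give no stopping rates, and Exploratory Outcome 8, unlike Exploratory Outcomes 1 to 3, does not specify a summary by treatment group. That effect is possible but not shown.

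Finally, Sections 11.4.4 and 11.4.4.3 leave exploratory efficacy detail to a separate statistical analysis plan, which is not in the text reviewed and may add a denominator. Even so, the outcome in Section 3.2.3 is defined as a count, and a plan that used a fraction would depart from it.

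**Conclusion.** The concern holds as a minor point. Followed as written, Exploratory Outcome 8 answers its adherence objective poorly because it has no denominator. Equal adherence gives counts 6 capsules apart at each of the Day 22 and Day 29 visits, mainly as noise between subjects. Required stops lower the Day 43 mean by 0.8 to 4.0 capsules if 2% to 10% stop after Day 22, and by 6.8 (84 − 77.2) if 10% stop after Day 8. These figures rest on assumed stopping rates, perfect intake otherwise and 42 days of dosing.

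Whether a required stop should count against adherence is a choice between total intake and intake while on drug. The plan has not made that choice, so saying that stopped subjects took every expected pill is true only once expected pills are defined to end at the stop.

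The primary analysis does not use this outcome. Its population is set by the 80% rule in Sections 3.2.1 and 11.4.1.

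**What to change.** In Section 3.2.3, replace the mean count with the percentage of expected capsules taken, by visit and arm: mean, median, quartiles and the share at or above 80%, in line with Section 3.2.1.

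Define expected capsules as those due from first dose to the earliest of the visit, the end of the planned dosing period, or a protocol-required stop. Report protocol-required stops separately. Alternatively, show the percentage both with and without the cut-off at the stop.

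Reconcile the durations in Sections 4 and 6.2, so that the Day 43 denominator is defined. Which duration applies is for the sponsor to state.

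The cost is one added derivation rule for stopped subjects and matching text in the statistical analysis plan. That rule is new, because neither Section 3.2.1 nor Section 11.4.1 says what is expected after a stop. It is proposed for this outcome only and leaves the per-protocol definition as it stands. No new data are needed: the visits already collect pill counts, and Section 11.4.1 already requires a cumulative fraction.
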